7.1 Study flow and visit schedule

Table 7-1 lists all of the assessments and indicates with an “X”, the visits when they are performed. All data obtained from these assessments must be supported in the patient’s source documentation.

Table 7-1 Visit evaluation schedule

	Screening/ Baseline Day -21 to C1D1	Cycle 1 Day 1	Cycle 1 Day 15 (+/- 3d)	Cycle 2 Day 1 (+/- 3d)	Cycle 2 Day 15 (+/- 3d)	Cycle 3 Day 1 (+/- 3d)	Cycle 5 Day 1 (+/- 3d)	Cycle 6 Day 1 (+/- 3d)	Cycle 7 Day 1 (+/- 3d)	Further cycles (+/- 3d)	Sympt omatic Progre ss ¹⁰	EOT	Follo w up	P&S Follow Up
Hematology, Biochemistry ⁸ Please document if clinically indicated/significant	X (fasting)	(X)*	X	X	X	X	X	X	X	X	X	X		
ECG ⁹	X (D-7 to -1) (anytime)		X (anytime)	X (anytime)	X (anytime)	X (anytime)	X (anytime)	X (anytime)				X (anytime)		
Urinalysis, Serum Lipid Profile, INR ⁸	X (fasting)													
Continuation of protocol														
Tumor evaluation: CT for chest, abdomen, pelvis	X ¹								X	(every 12 weeks)	X	(X) ^{2,5}		(X) ^{2,5}
Tumor evaluation: CT / MRI for Brain if clinically indicated	(X) ¹								(X) ²	(every 12 weeks) ²	(X) ²	(X) ^{2,5}		(X) ^{2,5}
Tumor evaluation: Bone Scan	X ³													
Tumor evaluation: Bone X-Ray / Bone CT, Skin lesion photography	(X) ⁴								(X) ⁴	(every 12 weeks) ⁴	(X) ⁴	(X) ^{2,5}		(X) ^{2,5}
Ribociclib/ letrozole (and goserelin) Dosing		Continuation of protocol												
Patient Diary		X		X		X								
EORTC QLQ-C30 & module BR-23		X		X		X								
Progression / survival status ⁷														P&S ⁷ X

Note: 1 Cycle = 28 days

*not necessary if last assessment was within 7 days before first intake of study medication.

§if EOT occurs for other reason than progression and patient withdraws consent for PFS follow up, if last tumor evaluation is older than 12 weeks.

¹Existing radiologic assessments can be used if assessed up to 28 days prior to C1D1. A corresponding RECIST evaluation should be performed and documented.

²If findings at baseline evaluation.

³Existing bone scans can be used if assessed up to 56 days prior to C1D1.

⁴Positive areas on bone scans must be assessed by X-ray or CT scan with bone windows on screening/baseline and should continue to be assessed using the same modality. (X-ray or CT scan with bone windows) every 12 weeks. Not all positive areas need to be followed up (non-target lesions) if significant and relevant tumor burden can be assessed by CT.

⁵All patients being discontinued from the study medication for other reasons than tumor progression (or death) should be scheduled for tumor evaluation at 12 week intervals after discontinuation until progression or LPLV occurs, whichever occurs first.

⁶Height is required only at baseline

⁷Survival information can be obtained via phone every 12 weeks, and information will be documented in the source documents and relevant eCRFs.

After the last patient in the trial has taken the last dose of Ribociclib, the post-antineoplastic treatment, current progression and survival status for all patients will be updated finally and recorded in the CRF.

⁸Existing assessment results can be used if assessed up to 21 days prior to C1D1.

⁹Excisiting ECG assessment can be used if it was within 7 days before first intake of study medication.

PPD

¹¹ For premenopausal patients; for postmenopausal patients, menopausal status should be confirmed according to local standard

7.1.1 Screening

The screening/baseline visit will occur maximum 21 days prior to first dose of the study drug ribociclib and starts with the signature of the individual ICF.

Patient must provide a signed Informed Consent Form (ICF) prior to any study specific screening evaluations.

The investigator must review inclusion/exclusion criteria and document the patient's eligibility in the patient record.

Re-screening of patients is only allowed once per patient if the patient was not registered as entering the treatment phase before (i.e. first study drug intake). In this case the Subject No. assigned to the patient initially will be used and the patient will be identified with this number throughout his/her entire participation to the study.

In case re-screening occurs, all evaluations re-assessed should meet the eligibility criteria. The following data will be collected for all screening failures:

- Informed consent signed
- Inclusion/exclusion (reason for failing)
- Demographics
- SAE data (if applicable).

7.1.1.1 Information to be collected on screening failures

Patients who signed the informed consent and are screened and do not meet all entry criteria will not be entered into the study. Such patients are considered to be screen failures. The reason for not being started will be entered in the site's screening failure log and on screening failure page in CRF.

7.1.1.2 Patient demographics and other baseline characteristics

The following assessments and procedures will be performed within 21 days prior the start of study treatment:

- Obtain patient's written informed consent form.
- General demography including age and gender.
- Medical history/current medical conditions (including prior concomitant medications within the last 4 weeks prior to Day 1).
- History and current disease status (including staging, diagnosis information, previous anti-cancer treatments and sites of disease). The following information must be collected for all previous anticancer therapies: date start, date end, setting (neoadjuvant, adjuvant, metastatic), best response, reason for treatment discontinuation.

Additionally, to determine eligibility at the screening visit, the following assessments will be performed:

- Physical examination, height and weight.
- Vital signs including blood pressure and heart rate.
- Existing ECG assessment can be used if it was within 7 days before first intake of study medication.
- ECOG performance status

- Safety laboratory assessments such as hematology, biochemistry, serum lipid profile, coagulation and urinalysis should be performed locally at the investigator's discretion and are not captured on the CRF. Laboratory assessments performed within 21 days prior to C1D1 may be used. If, at screening, laboratory results are out of range and clinically significant, these results should be captured on the medical history/current medical conditions CRF.
- Radiological tumor assessments at baseline:
 - CT for chest abdomen and pelvis unless performed within 28 days prior to C1D1. CT scan with contrast media should be used except for patients who are allergic/sensitive to the radiographic contrast media. CT for chest and abdomen may be replaced by MRI if clinically contraindicated, e.g. allergy/sensitivity to the radiographic contrast media, metastatic presentation, after prior consultation and approval by Novartis.
 - Brain: CT or MRI if CNS metastases are present unless performed within 28 days prior to C1D1.
 - Whole Body Bone Scan unless performed within 56 days prior to C1D1.

7.1.2 Treatment period

Ribociclib will be dosed starting on treatment Day 1 (Visit 2). Patients will be instructed to take 3 tablets of 200 mg ribociclib orally with a large glass of water, once daily at the same time each day with or without food for 21 days, followed by 7 days without taking ribociclib. Patients will be instructed to inform the investigator of the date of first ribociclib study drug intake.

Letrozole will be dosed starting on treatment Day 1 (Visit 2). Patients will be instructed to take 1 tablet of 2.5 mg letrozole orally with a large glass of water at the same time each day in the morning. Package insert instructions should be followed.

For premenopausal women and men, goserelin will be subcutaneously injected on Day 1 of each cycle. Package insert instructions should be followed.

Patients will continue to be treated per protocol until documentation of disease progression, unacceptable toxicity, death or discontinuation due to any other reason. Treatment beyond progression is at the discretion of the investigator. Information on drug exposure will be collected on the Dosage Administration Record page of the eCRF.

For details of assessments, refer to Table 7-1. The investigator and/or study personnel will assess compliance at each patient visit.

7.1.3 End of treatment visit including study completion and premature withdrawal

At the time patients discontinue study treatment a visit should be scheduled no more than 7 days later, at which time all of the assessments listed for the End of Treatment (EOT) visit will be performed. An End of Treatment Phase Disposition CRF page should be completed, giving the date and reason for stopping the study treatment.

At a minimum, all patients who discontinue study treatment, including those who refuse to return for a final visit, will be contacted for safety evaluations during the 30 days following the last dose of study treatment.

Patients who discontinue study treatment for other reasons than progression also should return for tumor assessments every 12 weeks until disease progression and should not be considered withdrawn from the study. If patients refuse to return for these visits or are unable to do so, every effort should be made to contact them or a knowledgeable informant by telephone to determine the progression of the disease.

If a study withdrawal occurs, or if the patient fails to return for visits, the investigator must determine the primary reason for a patient's premature withdrawal from the study and record this information on the End of Treatment Disposition CRF page.

If a patient discontinues study treatment, but continues study assessments, the patient remains on study until such time as he/she completes protocol criteria for ending study assessments. At that time, the reason for study completion should be recorded on the Study Phase Completion Disposition CRF (SEC) page.

End of treatment/Premature withdrawal visit is not considered as the end of the study.

7.1.3.1 Study completion

The end of treatment (LPLT=EOT) for all patients is planned 80 weeks after the first intake of ribociclib of the last patient (LPFT) or progression of disease of all patients, whichever occurs first. Patients will be followed for safety for 30 days after the individually last dose of study drug to achieve the end of study (LPLV). After last patient last treatment (LPLT), the post-antineoplastic treatment, the current progression and survival status for all patients will be updated finally and recorded in the eCRF.

7.1.3.2 Criteria for premature patient withdrawal

Patients may voluntarily withdraw from the study or be dropped from it at the discretion of the investigator at any time.

Patients must be withdrawn from the study treatment if any of the following occur:

- Pregnancy
- Subject decision
- Lost to follow up

7.1.4 Follow up period

All patients must be followed for 30 days after the last dose of study drug for safety assessment (AEs and/or SAEs).

All new anticancer therapies given after the last dose of the study drug ribociclib will be recorded on eCRF pages designed to capture antineoplastic therapies within 30 days following discontinuation from the study.

All patients being discontinued from the study medication for other reasons than tumor progression (or death) should be scheduled for tumor evaluation at 12 week intervals after discontinuation until progression or LPLV occurs, whichever occurs first.

Survival status and the current progression will be updated for all patients finally and recorded in the eCRF after last patient last treatment (LPLT) until LPLV. Survival information can be obtained via phone, and information will be documented in the source documents and relevant eCRFs.

Patients lost to follow up should be recorded as such on the CRF. For patients who are lost to follow-up, the investigator should show “due diligence” by documenting in the source documents steps taken to contact the patient, e.g., dates of telephone calls, registered letters, etc.

7.1.5 Survival follow up

All patients will be followed up for survival status every 12 weeks regardless of treatment discontinuation reason until death, lost to follow-up, or withdrawal of consent to survival follow-up. Additional survival assessments may be performed outside the 12 weeks follow up schedules if a survival is required for an interim assessment to meet safety or regulatory needs.

Survival information can be obtained via phone, and information will be documented in the source documents and relevant eCRFs.

7.2 Assessment types

7.2.1 Efficacy assessments

Tumor assessment and response will be evaluated according to RECIST (Version 1.1) (Protocol Post-text Supplement: 1). All radiologic assessments must be performed within a +/- 7 day window of the visit.

Patients should have either at least one lesion that can be measured as per RECIST criteria OR have bone lesions: lytic or mixed (lytic + sclerotic) in the absence of measurable disease OR have non-measurable disease.

For patients with measurable disease at screening (as per RECIST criteria), tumor progression will be evaluated every 12 weeks until progression or End of study, whichever is first (according to the RECIST 1.1 criteria). All tumor evaluations performed routinely in addition to the above mentioned will be evaluated and documented according to RECIST 1.1 as well. All patients being discontinued from the study for disease progression must have their progression documented using the criteria specified in RECIST 1.1.

Bone scans must be performed at screening within 56 days before C1D1. Positive areas on bone scans must be assessed by X-ray or CT scan with bone windows, prior to C1D1 and should continue to be assessed using the same modality (X-ray or CT scan) every 12 weeks until progression or End of study. Additional bone scans should be performed if clinically indicated. Abnormalities found on subsequent bone scans must be confirmed by X-ray or CT scan. Bone scans may be replaced by whole body CT, provided that this is local standard. The whole-body CT must be performed within a +/- 7 days window of the visit.

Color photography, including a metric ruler to estimate the size of the lesion, must be acquired for all skin lesions present at baseline. These should be followed throughout the study according to the schedule outlined in Table 7-1.

All patients being discontinued from the study for other reasons than tumor progression (or death) should be scheduled for tumor evaluation at 12 week intervals after discontinuation until LPLV occurs.

The same method of assessment and the same technique should be used to characterize each identified and reported lesion at baseline for each study tumor assessment after start of study treatment.

Response will be assessed by local radiology review. The decision regarding patient management will remain with the local investigator, there will be no central review in this study. The same radiologist/physician should perform the evaluation for each individual patient for the entire duration of the study.

A CT scan of the chest, abdomen and pelvis will be performed at screening (≤ 4 weeks prior to the first dose of Ribociclib) and periodically as indicated in [Table 7-1](#). CT Scans with contrast media should be used except for patients who are allergic/sensitive to the radiographic contrast media.

All patients should have at least one lesion that can be accurately measured in at least one dimension ≥ 10 mm with conventional imaging techniques or ≥ 10 mm with spiral CT OR bone lesions such as lytic or mixed (lytic + sclerotic) in the absence of measurable disease OR other lesions, including small lesions (longest diameter <20 mm with conventional techniques or <10 mm with spiral CT scan), i.e., leptomeningeal disease, ascites, pleural/pericardial effusion, lymphangitis cutis/pulmonis, cystic lesions, and also abdominal masses that are not confirmed and followed by imaging techniques.

For patients with measurable disease at baseline, progression will be determined according to the RECIST 1.1 criteria (see Appendix 14.2. for details).

In the absence of measurable disease at baseline, the following will be considered progression among patients with lytic or mixed (lytic + sclerotic) bone lesions:

- The appearance of one or more new lytic lesions in bone
- The appearance of one or more new lesions outside of bone
- Unequivocal progression of existing bone lesions

Note: Pathologic fracture, new compression fracture, or complications of bone metastases will not be considered as evidence of disease progression, unless one of the above-mentioned criteria is fulfilled.

Non measurable disease:

Complete Response (CR) is considered as disappearance of all non-target lesions. All lymph nodes must be non-pathological in size (<10 mm short axis).

NCRNPD is considered as persistence of one or more non-target lesion(s).

Progressive Disease (PD) is considered as appearance of one or more new lesions and/or unequivocal progression of existing non-target lesions. Unequivocal progression should not normally trump target lesion status. It must be representative of overall disease status change, not a single lesion increase.

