2.4.4 New lesions

The appearance of a new lesion is always associated with Progressive Disease (PD) and has to be recorded as a new lesion in the New Lesion CRF page:

- If a new lesion is **equivocal**, for example because of its small size, continued therapy and follow-up evaluation will clarify if it represents truly new disease. If repeat scans confirm there is definitely a new lesion, then progression should be declared using the date of the first observation of the lesion.
- If new disease is observed in a region which was **not scanned at baseline** or where the particular baseline scan is not available for some reason, then this should be considered as a PD. The one exception to this is when there are no baseline scans at all available for a patient in which case the response should be UNK, as for any of this patient's assessment (see [Section 2.5](#)).
- A **lymph node is considered as a “new lesion”** and, therefore, indicative of progressive disease if the short axis increases in size to ≥ 10 mm for the first time in the study plus 5 mm absolute increase.

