5.1 Definition of efficacy variables

Progression:

1. ds.eotdreasn = 4 (Main reason for ribociclib discontinuation = progressive disease)
2. ds.eotprdi1n = 1 (Radiologic progression according to RECIST 1.1) OR
3. ds.eotprdi3n = 1 (Clinically symptomatic progress) OR
4. zr.recoveran = 4 (Overall lesion response = Progressive Disease) OR
5. zr.recnewln=1 (New Lesion)

Progression date:

1. ds.eotcprdt (date of clinically symptomatic progress) OR
2. Date of Evaluation where zr.recoveran = 4 or zr.recnewln = 1

Response:

3. zr.recoveran (Overall lesion response)

Assessment Date:

4. zr.tlesdt (Date of image or examination, Target Lesion Assessment)
5. zr.ntlesdt (Date of image or examination, Non-Target Lesion Assessment)
6. zr.nlesdt (Date of image or examination at which new lesion appeared)

Date of Death:

7. sc.deathdt

Date of last contact:

8. sc.eoslcdt

Start of treatment = first administration of Ribociclib or Letrozole:

9. min(min(zq.ribostdt), min(zq.letrstdt))

5.1.1 Clinical Benefit Rate (CBR) until week 24

Best overall response in (CR, PR, SD, NCRNPD):

1. zr.recoveran = 1; at least two determinations of CR at least 4 weeks apart before progression OR
2. zr.recoveran = 2; at least two determinations of PR or better at least 4 weeks apart before progression (and not qualifying for a CR)
3. zr.recoveran = 3; two determinations of SD at least 12 weeks apart (and not qualifying for PR or PD)

4. zr.recoveran = 5

Tumor evaluations are scheduled for baseline, Cycle 4 and cycle 7 etc. (every 12 weeks). Thus, to assess the CBR at week 24 the first two post-baseline evaluations have to be considered. Additionally it has to be checked that no progression occurred during the following 4 weeks. Deviations against the time schedule is investigated and assessed during the data review meeting.

5.1.2 Overall response rate (ORR) by week 24

Similar to 5.1.1, but the best overall response must be in in (CR, PR)

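### For lytic or mixed bone disease without measurable lesions, Protocol 7.2.1 and Appendix 2/SAP 5.1 define progression differently, so a new sclerotic bone lesion can be a CBR success or a progression

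*Protocol*

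**What the plan says.** Protocol 7.2.1 first sends patients with measurable disease to RECIST 1.1 as set out in Appendix 14.2. It then gives a separate list for patients without measurable disease: "the following will be considered progression among patients with lytic or mixed (lytic + sclerotic) bone lesions". The list has three entries:

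- in bone: "The appearance of one or more new lytic lesions in bone";
- elsewhere: "The appearance of one or more new lesions outside of bone";
- clear worsening of bone lesions already present.

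A note excludes fractures and other bone complications as evidence of progression "unless one of the above-mentioned criteria is fulfilled". A new purely sclerotic bone lesion is not on the list.

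Protocol Appendix 2, section 2.4.4, makes no distinction by lesion type: "The appearance of a new lesion is always associated with Progressive Disease (PD) and has to be recorded as a new lesion". Table 3-1 of the same appendix, for patients with non-target disease only, assigns PD to any non-target status combined with a new lesion. Protocol 10.4.1 derives best overall response under RECIST 1.1 and points to that appendix without a bone exception.

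SAP 5.1 programs progression from several fields, one of which is "zr.recnewln=1 (New Lesion". The same flag also supplies a progression date. SAP 5.1.1 counts an investigator overall response of NCRNPD (zr.recoveran = 5) as clinical benefit. SAP section 4, on changes to the protocol's analyses, does not mention the bone list.

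**The concern.** The two rules classify the same scan in opposite ways, and the classification feeds the primary endpoint. There is no central review and about 100 centres are planned, so one site may follow the bone list while another follows the appendix.

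The SAP can also disagree with itself. A site that follows 7.2.1 may record NCRNPD and still complete the new-lesion page, as Appendix 2 requires. The assessment then holds zr.recoveran = 5, a success category, and zr.recnewln = 1, a progression. No precedence rule is given. Yet Appendix 2 section 3.1 bases best overall response on the investigator's review, and section 4.4 says that this assessment is not to be overruled.

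At stake is a consistent event definition for week-24 CBR and for PFS in this group of patients.

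**Working it through.** **Step 1: compare the rules.** Take a patient with lytic or mixed bone lesions, no measurable disease, one new purely sclerotic bone lesion, and no other change.

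| Source | New sclerotic bone lesion counts as PD? | Result |
|---|---|---|
| Protocol 7.2.1, bone list | Not listed | NCRNPD, CBR success |
| Appendix 2, section 2.4.4 | Yes, any new lesion | PD |
| Appendix 2, Table 3-1 | Yes, any new lesion | PD |
| SAP 5.1, new-lesion flag | Yes, if the flag is set | Progression |
| SAP 5.1.1, investigator response field | Depends on what the site recorded | Success if zr.recoveran = 5 |

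**Step 2: when it matters.** SAP 5.1.1 uses the first two post-baseline evaluations and then checks the following 4 weeks for progression. A sclerotic lesion seen in that window changes CBR and PFS. One seen later changes PFS only. Duration of response is hardly touched: it covers patients with CR or PR, and Table 3-1 allows no PR in non-target-only disease, so only a confirmed CR could bring such a patient in.

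**Step 3: yardstick.** The sample size sections (Protocol 10.8, SAP section 3) give 75.4% to 82.6% for a CBR of 79% with N = 500. This reproduces as

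0.79 ± 1.96 × √(0.79 × 0.21 / 500) = 0.79 ± 1.96 × 0.0182 = 0.79 ± 0.036.

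The standard error is 1.8 points and the half-width 3.6 points. The unrounded width is 7.1; the stated 7.2 is the difference of the rounded limits. The Clopper-Pearson interval for 395/500 is 75.2% to 82.5%.

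**Step 4: illustration of size.** Inputs:

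- Bone-only share 22.0%, from the pivotal trial as reported in Protocol 1.2.6. It stands in for the affected share here: 0.22 × 500 = 110 patients.
- Share f of these with a new purely sclerotic lesion as the only change in the CBR window. The documents give no figure; 2% to 20% is an assumption.
- All such patients would otherwise be CBR successes.

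Shift in total CBR = 0.22 × f.

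| f | Patients (110 × f) | Shift (points) | CBR, starting from 79.0% |
|---|---|---|---|
| 2% | 2.2 | 0.4 | 78.6% |
| 5% | 5.5 | 1.1 | 77.9% |
| 10% | 11 | 2.2 | 76.8% |
| 20% | 22 | 4.4 | 74.6% |

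If only half of the 22% were in the affected category (again an assumption), the shifts would halve, to 0.2 to 2.2 points.

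**The case against.** The strongest reply is that the hierarchy is already clear. Section 7.2.1 opens by placing all tumor assessment under RECIST 1.1, the endpoint is defined by RECIST 1.1, and 10.4.1 refers to Appendix 2, which SAP 5.1 follows. That is a fair account of where the analysis points. It leaves the bone list with no function, however. Since 7.2.1 refers only measurable-disease patients to the appendix, a site could reasonably take the list as a deliberate exception. If it is one, 10.4.1 and the SAP do not carry it.

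It can also be said that the list does not use the word only, and that its note concerns fractures. That is correct. But a list that specifies lytic for new lesions in bone and applies no such limit outside bone invites the narrower reading.

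Two stronger readings are tempting and are not supported:

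- *That 7.2.1 contradicts itself.* Its later paragraph on non-measurable disease says "Progressive Disease (PD) is considered as appearance of one or more new lesions and/or unequivocal progression of existing non-target lesions". The section may be following the three eligibility categories in Protocol 5.2, criterion 9, where non-measurable disease, including osteoblastic bone lesions, is listed separately from lytic or mixed bone disease. An internal contradiction is therefore not established. The conflict with Appendix 2 and SAP 5.1 does not depend on it.
- *That all bone-only patients are affected.* Patients with blastic lesions only fall in that separate category, where any new lesion is PD in every source.

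The objection to the numbers also stands in part. The 22.0% comes from a first-line postmenopausal population with ECOG 0 or 1. It is not split by lesion type, and it may include blastic-only patients or lytic lesions with a measurable soft-tissue part. Appendix 2 also lets equivocal new lesions be followed before PD is declared, which would reduce the count.

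**Conclusion.** The documents hold two progression rules for patients with lytic or mixed bone lesions and no measurable disease, and they give opposite results when a new purely sclerotic bone lesion is the only change. The SAP can carry both results for one assessment without saying which prevails. This is an inconsistent event definition for the primary endpoint and for PFS, worth correcting although the trial only estimates and tests no hypothesis.

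The size is unknown. Under the assumptions above, total CBR would move by about 0.4 to 4.4 points. At 2% or 5% the shift is below one standard error (1.8 points); at 10% it is above; at 20% it exceeds the half-width of the planned interval (3.6 points). A reader might infer that CBR is materially biased. The documents do not support that, because they give neither the rate of such lesions nor the size of the affected group. Nor do they settle which rule is right.

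**What to change.** - Reconcile Protocol 7.2.1, Appendix 2 (section 2.4.4 and Table 3-1) and SAP 5.1, so that one progression rule applies to patients with lytic or mixed bone lesions and no measurable disease. The choice is the sponsor's. It bears on the RECIST 1.1 definition of the endpoint, and progression also governs the stopping of treatment.
- State in SAP 5.1 which field prevails when the investigator's overall response and the new-lesion flag disagree.
- At data review, list and query assessments with zr.recoveran = 5 and zr.recnewln = 1. Query the type of new bone lesions in this subgroup, since the SAP names a flag and a date for new lesions but no lesion type.
- Report CBR and PFS under the other rule as a sensitivity analysis, with the number of patients reclassified.

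Cost: wording in two documents, one extra analysis, and a lesion-type query confined to new bone lesions in this subgroup. Enrollment is complete, so the change acts on how assessments are analysed and does not alter those already made.
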